**I. OBJECTIVES**

***Phase I***

**Primary:**

Determine the MTD of clofarabine to be used in portion II of the study.

***Phase II***

**Primary:**

Compare the response rates of two different regimens CIA versus FLAI

**Secondary:**

Evaluate the durability of response, the overall and event-free survival rates, and the safety profile of 2 different regimens.

**II. RATIONALE**

Treatment options for relapsed and refractory AML and high-risk MDS are limited.

Retreatment with a high-dose cytarabine (HDAC) containing regimen is considered standard for patients relapsing after an initial complete remission (CR) lasting for a year or more. Once a second remission is achieved, these patients can proceed to stem cell transplant if appropriate donors are available. For patients relapsing after a shorter

remission or with primary refractory disease no true standard options exist and investigational therapy is considered appropriate.

We have been using fludarabine and ara-C (FA) combination chemotherapy since 1989 for relapsed AML, and since 1991 for newly diagnosed AML/MDS. We have reported that FA is superior to ara-C in relapsed AML, if disease is sensitive to ara-C as manifested by a relatively long first remission. In patients with newly diagnosed disease, the use of FA- containing regimens was associated with higher complete response rates (50-60%) than with standard chemotherapy. The effectiveness of FA is believed due to the ability of fludarabine to modulate the pharmacologic behavior of ara-C. Specifically, at intracellular concentrations of  $\geq 10 \mu\text{M}$ , F-ara-ATP, the active metabolite of fludarabine, increases accumulation of ara-CTP in AML cells beyond that possible with dose escalation of ara-C. Once above  $10 \mu\text{M}$  F-ara-ATP, ara-CTP formation plateaus.

Single agent clofarabine has demonstrated activity in phase I studies in AML. As a potent inhibitor of ribonucleotide reductase (RNR) and by means of biochemical modulation, clofarabine is more ideally suited to be incorporated into combinations such as have been tested and validated with fludarabine and cytarabine in AML in the past. We have previously conducted a study combining cytarabine with clofarabine in patients with relapsed/refractory AML. At doses of  $1 \text{ g/m}^2$  daily x 5 for cytarabine and  $40 \text{ mg/m}^2$  daily x 5 for clofarabine, we reported a response rate of 40% (28% complete remission) in 29 patients with a median age of 59 years (18 to 84 years). Responses extended to

patients with primary refractory disease and those with abnormal cytogenetics. Other groups have since followed this lead and published comparable results, albeit doses of cytarabine and clofarabine varied throughout the different studies.

Anthracyclines have been traditionally combined with cytarabine in AML. Two recent publications highlighted higher response rates and better disease-free survival in both younger and older patients with frontline AML when high-dose daunorubicin (90 mg/m^2/dose) was used in a “3+7” induction combination highlighting the activity of this class of agents for AML therapy. Pautas et al randomized 468 patients ages 50 to 70 years on Acute Leukemia French Association studies to 3 induction anthracycline regimens: idarubicin 12 mg/m^2 daily for 3 days, idarubicin 12 mg/m^2 daily for 4 days, and high-dose daunorubicin 80 mg/m^2 daily for 3 days. The CR rate with idarubicin daily for 3 days was higher than with high-dose daunorubicin (83% vs 70%), as was the 3-year event-free survival rate (23% vs 16%).

The combination with nucleoside analogs synergizes the anthracyclines activity by inhibiting DNA repair damage. Holowiecki et al from Poland randomized 673 patients (ages 18 to 60 years) to receive either daunorubicin plus cytarabine (DA), or DA plus fludarabine, or DA plus chlorodeoxyadenosine (DAC). The authors reported significantly higher CR rates after 1 course of induction and overall and reported better 3-year survival rates with the addition of the DAC regimen.

We have previously explored the combination of clofarabine, idarubicin, and cytarabine in a phase I study for patients with relapsed/refractory AML. The following doses were established for further evaluation: clofarabine 22.5 mg/m^2 daily x 5, idarubicin 6 mg/m^2 daily x 3, and cytarabine 0.75 mg/m^2 daily x 5. In a recent update of a phase II study of 63 patients treated with CIA, the overall response rate was 38% including 21% with complete remission. Median overall survival was 34 weeks for all patients and 66 weeks for those patients who achieved CR/CRp. Twenty-four patients (38%) were able to proceed with a stem cell transplant. Induction mortality was at 8%. Toxicities were manageable.

In view of this experience and in light of above data of the possible usefulness of higher doses of anthracyclines, and the synergistic activity of the combination of anthracyclines with nucleoside analogues, we propose to evaluate in a phase II Bayesian design the CIA combination at higher doses than established versus the FLAI combination in patients with relapsed/refractory and newly diagnosed AML (not fit for any protocol) and high-risk MDS.

### **III. BACKGROUND DRUG INFORMATION**

#### **A. Idarubicin:**

Idarubicin is commercially available.

#### **Mechanism of action:**

Similar to doxorubicin and daunorubicin; inhibition of DNA and RNA synthesis by intercalation between DNA base pairs.

**Adverse effects:**

- Cardiovascular: Transient EKG abnormalities (supraventricular tachycardia, S-T wave changes, atrial or ventricular extrasystoles); generally asymptomatic and self-limiting. Congestive heart failure, dose-related. The relative cardiotoxicity of idarubicin compared to doxorubicin is unclear. Some investigators report no increase in cardiac toxicity at cumulative oral idarubicin doses up to 540 mg/m^2; other reports suggest a maximum cumulative intravenous dose of 150 mg/m^2.
- Central nervous system: Headache
- Dermatologic: Alopecia (25% to 30%), radiation recall, skin rash (11%), urticaria
- Gastrointestinal: Nausea, vomiting (30% to 60%); diarrhea (9% to 22%); stomatitis (11%); GI hemorrhage (30%)
- Genitourinary: Discoloration of urine (darker yellow)

**B. Cytarabine**

Cytarabine is commercially available.

**Mechanism of action:**

Cytarabine is an antimetabolite. Cytarabine is cell cycle–specific for the S phase of cell division. Activity occurs as the result of activation to cytarabine triphosphate in the tissues and includes inhibition of DNA polymerase and incorporation of cytarabine into DNA and RNA.

**Adverse effects:**

**COMMON**

- Cardiovascular: Thrombophlebitis

- Dermatologic: Rash, conjunctivitis
- Endocrine metabolic: Hyperuricemia
- Gastrointestinal: Anal inflammation, Diarrhea, Loss of appetite, Nausea, Stomatitis, Ulcer of anus, Ulcer of mouth, Vomiting
- Hematologic: Decreased reticulocyte count, Megaloblastic anemia
- Hepatic: Decreased liver function
- Other: Fever

### **SERIOUS**

- Hematologic: Anemia, Bleeding, Leukopenia, Thrombocytopenia
- Immunologic: Anaphylaxis
- Neurologic: Neuropathy
- Renal: Kidney disease
- Other: Infectious disease, Sepsis

### **C. Fludarabine**

Fludarabine is commercially available.

#### **Mechanism of action:**

Fludarabine phosphate is fluorinated nucleotide and analog of antiviral agent vidarabine, that is relatively resistant to adenosine deaminase deamination. It is actively dephosphorylated to 2-fluoroara-A and phosphorylated further by deoxycytidine kinase to 2-ribonucleotide reductase and DNA primase resulting in DNA synthesis inhibition.

#### **Adverse effects:**

### **COMMON**

- Endocrine metabolic: Shivering
- Gastrointestinal: Loss of appetite, Nausea, Vomiting
- Neurologic: Asthenia
- Other: Fatigue, Malaise

### **SERIOUS**

- Cardiovascular: Edema (frequent)
- Dermatologic: Aplasia of skin (rare)
- Hematologic: Autoimmune hemolytic anemia, Graft versus host disease, Transfusion-associated, with non-irradiated blood (rare), Myelosuppression (frequent)
- Neurologic: Neurotoxicity
- Respiratory: Pneumonia (frequent)
- Other: Fever (frequent), Infectious disease

### **D. Clofarabine**

Clofarabine is commercially available.

#### **Mechanism of action:**

Clofarabine potently inhibits DNA synthesis by inhibiting both DNA polymerase and ribonucleotide reductase. Clofarabine demonstrated the ability to disrupt mitochondrial integrity that results in the release of pro-apoptotic proteins, cytochrome C and apoptosis-inducing factor.

#### **Adverse effects:**

- Hematologic: Myelosuppression, infections

- Hepato and Gastrointestinal: Nausea/vomiting, diarrhea, mucositis, stomatitis/pharyngitis, hyperbilirubinemia, increase of SGPT and/or SGOT, abdominal pain or cramping, peritonitis, pancreatitis, liver failure
- Dermatologic: Skin rash with blisters (particularly hand-foot syndrome), Steven-Johnson's syndrome, alopecia, conjunctivitis
- Systemic: Fatigue, asthenia, anorexia, lethargy, malaise, mental status changes/coma, alopecia
- Allergic reactions: (including fever, muscle aches, edema, dyspnea)
- Cardiology: Congestive heart failure
- Nephrology: Kidney failure
- Autoimmune reactions: (antiplatelet antibodies, erythema nodosum) and/or chemical imbalances in the blood.

#### **IV. Eligibility criteria**

##### **Inclusion criteria:**

- Sign an IRB-approved informed consent document.
- Age 18 to 60. Patients above the age of 60 only with PI approval
- Diagnosis of newly diagnosed AML [other than acute promyelocytic leukemia (APL)]. Prior therapy with hydrea and the use of a single or a two day dose of cytarabine (up to 3 g/m^2) for emergency use up to 24 hours prior to start of study therapy is allowed. Prior therapy for MDS or other AHD is not allowed.
- ECOG performance status of ≤ 3 at study entry.
- Organ function as defined below (unless due to leukemia):

- Serum creatinine  $\leq 3$  mg/dL
- Total bilirubin  $\leq 2.5$  mg/dL
- ALT (SGPT)  $\leq 3$  x ULN or  $\leq 5$  x ULN if related to disease
- Women of childbearing potential must have a negative serum or urine pregnancy test within 7 days. Men must agree not to father a child and agree to use a condom if his partner is of child bearing potential.
- Cardiac ejection fraction  $\geq 40\%$  (by either cardiac echo or MUGA scan).  
Documentation of recent ( $\leq 6$  months from screening) outside reports is acceptable.

**Exclusion Criteria:**

- Breast feeding females
- Patients with uncontrolled active infections (viral, bacterial, and fungal are not eligible).
- Patients with active secondary malignancy will not be eligible.

**IV. Treatment plan**

**1. Study design**

The study will include a phase I portion to determine MTD dose of clofarabine to be used in the subsequent randomized phase II portion. Patients will be randomized to either arm on an even basis at the beginning, then, based on efficacy and following a Bayesian design, patients will be assigned to the superior arm.

**2. Induction**

**2.1 Phase I (fixed dose of idarubicin of 10 mg/m^2 day 1-3 and cytarabine 1 g/m^2 day 1-5)**

Clofarabine IV over approximately 1 hour daily for 5 days (days 1-5). Dose levels and dose escalation schema are described below.

Idarubicin 10 mg/m^2 IV over approximately 30 minutes daily for 3 days (days 1-3)

Cytarabine 1 g/m^2 IV over approximately 2 hours daily for 5 days (days 1-5)

Idarubicin will follow clofarabine by 1 to 2 hours and cytarabine will follow clofarabine by 3 to 6 hours. All chemotherapeutic agents will be dosed, prepared, and administered according to MDACC institutional guidelines. BSA will be recalculated prior to each subsequent course.

Patients will be entered sequentially to each dose level. If none of the first 3 patients at a dose level experience first cycle dose-limiting toxicity (DLT), new patients may be entered at the next higher dose level. If 1 of 3 patients experience first cycle DLT, up to 3 more patients are started at that same dose level. If 2 or more experience first cycle DLT, no further patients are started at that dose and clofarabine's dose will be reduced to -1 level, which is 10 mg/m^2 IV daily for 5 days. The MTD is the highest dose level in which <2 patients of 6 develop first cycle DLT. New dose levels may begin accrual only if all patients at the current dose level have been observed for a minimum of 4 weeks.

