**Dose escalation schedules are as follows:**

Dose level	Clofarabine (mg/m^2 IV daiy for 5 days)
-1	10
1 Starting	15
2	20
3	25
4	30

A DLT is defined as a clinically significant adverse event or abnormal laboratory value assessed as unrelated to disease progression, intercurrent illness, or concomitant medications and occurring during the first course on study that meets any of the following criteria:

- CTCAE Grade 3 AST (SGOT) or ALT (SGPT) for > 7 days
- CTCAE Grade 4 AST (SGOT) or ALT (SGPT) of any duration
- All other clinically significant NCI common terminology criteria that are CTCAE Grade 3 or 4

An AE must be clinically significant to define DLT e.g. alopecia, study drug-related fever, electrolyte abnormalities (including K, Na, Cl, HCO3, Mg, Ca) that are < Grade 3 will not define the DLT. Drug-related Grade 3-4 nausea and vomiting not controlled with adequate therapy and Grade 3-4 hyperbilirubinemia will be considered DLTs. Only prolonged myelosuppression, as defined by the NCI criteria specific for leukemia, i.e. marrow cellularity <5% on day 42 or later (6 weeks) from start of therapy without evidence of leukemia, will be considered in defining the MTD and DLT.

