## 2.2 Phase II

In the Phase II portion, patients will randomized to receive

a. Clofarabine (dose selected based on Phase I portion) IV over approximately 1 hour daily for 5 days (days 1-5)

b. Idarubicin  $10 \text{ mg/m}^2$  IV over approximately 30 minutes daily for 3 days (days 1-3)

c. Cytarabine  $1 \text{ g/m}^2$  IV over approximately 2 hours daily for 5 days (days 1-5)

Idarubicin will follow clofarabine by 1 to 2 hours and cytarabine will follow clofarabine by 3 to 6 hours.

**or**

a. Fludarabine  $30 \text{ mg/m}^2$  IV over approximately 30 minutes daily for 5 days (days 1-5)

b. Idarubicin  $10 \text{ mg/m}^2$  IV over approximately 30 minutes daily for 3 days (days 1-3)

c. Cytarabine  $1 \text{ g/m}^2$  IV over approximately 2 hours daily for 5 days (days 1-5)

Idarubicin will follow fludarabine by 1 to 2 hours and cytarabine will follow fludarabine by 3 to 6 hours.

The induction or reinduction may be given over 4 days (Fludarabine, Clofarabine and Cytarabine) in patients  $\geq 65$  years, or at the discretion of the treating physician and over 3 days (Fludarabine, Clofarabine and Cytarabine) in patients with PS  $\geq 2$ , or at the discretion of the treating physician. Idarubicin  $8\text{-}10 \text{ mg/m}^2$  will be given for 2 days in these situations.

Patients, who have not achieved a complete remission following one induction course can receive a second induction course to optimize response if possible. A second induction course at the same dose as the previous course or in a dose-reduced fashion

should not be given until at least 28 days of course 1. If the bone marrow aspirate and/or biopsy(s) performed after the re-induction cycle reveals a remission marrow (CR/CRp), then the patient may proceed with consolidation at the discretion of the treating investigator. In addition, any clinically significant drug-related, non-hematologic toxicity experienced by a patient should return to  $\leq$  grade 2 or the baseline grade before the patient continues treatment. Should the patient not have achieved a remission after the reinduction course, he will be taken off study for failure to respond, unless the patient has achieved clinical benefit or partial remission, at which time further therapy on protocol may be permitted with approval from the PI.

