### During therapy

1. CBC, differential, and platelet count every 3-7 days (the differential may be omitted when the WBC is  $\leq 500$ .)
2. Creatinine, bilirubin, ALT or AST once weekly.
3. Marrow aspirate to confirm complete remission.

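### The Phase I rules send dosing to 10 mg/m² after failure at any level, give a level cleared at 0/3 no stated route to the 6 patients the MTD needs, and allow escalation before the day-42 DLT can be scored

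*Combined protocol and SAP*

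**What the plan says.** Treatment plan section 2.1 escalates clofarabine over 15, 20, 25 and 30 mg/m² (levels 1 to 4), with level -1 at 10 mg/m². Idarubicin and cytarabine doses are fixed.

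- **0/3 DLTs:** the next level may open.
- **1/3:** "If 1 of 3 patients experience first cycle DLT, up to 3 more patients are started at that same dose level".
- **2 or more:** "no further patients are started at that dose and clofarabine's dose will be reduced to -1 level". The same sentence gives that level as 10 mg/m².
- **MTD:** "The MTD is the highest dose level in which <2 patients of 6 develop first cycle DLT".
- **Timing:** a new level may accrue "only if all patients at the current dose level have been observed for a minimum of 4 weeks".

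Under the DLT definition that follows the dose table, myelosuppression counts only if prolonged: "marrow cellularity <5% on day 42 or later (6 weeks) from start of therapy without evidence of leukemia".

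Section V (During therapy) asks for "CBC, differential, and platelet count every 3-7 days" and for "Marrow aspirate to confirm complete remission". The first is frequent; the second carries no date in that list. The only dated on-therapy marrow in the accompanying table is day 28 ± 7.

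Section X (Phase I) names a 3+3 design with four dose levels and at most 24 patients, and refers to section 2.1 for the detailed rules.

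**The concern.** Finding the MTD is the only Phase I objective, and the MTD becomes the clofarabine dose of the randomized CIA arm. The Rationale (section II) aims to test CIA at doses above those already established. The earlier clofarabine dose was 22.5 mg/m², given with idarubicin 6 mg/m² rather than 10.

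If failure at a high level sends dosing to the bottom of the ladder, and the level just below the failed one stays at 3 patients, the trial may carry forward too low a dose or have no dose that meets its own definition.

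The timing question concerns patient exposure. If a higher level opens before prolonged aplasia at the level below can be recognized as a DLT, patients may be treated at a dose that a complete assessment would have held back. The Phase II toxicity stopping rule in section X counts only non-hematological events, so Phase I is where a formal rule judges this toxicity.

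**Working it through.** **Inputs.** Dose levels, DLT definition, escalation rules and the 4-week minimum: Treatment plan section 2.1. Cap of 24 and the 3+3 label: section X, Phase I. Marrow and blood count schedule: section V. Earlier dose of 22.5 mg/m²: section II.

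**1. The plan's own figure.** Four levels × 6 patients = 24, which matches the stated maximum. This is what a conventional 3+3 with up to 6 patients per level would give.

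**2. Where the de-escalation rule sends the dose.** Level -1 is named as 10 mg/m², so it cannot be read as one level down. Nothing limits the step to failure at level 1.

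| Failed level (mg/m²) | One level down | As written | Levels skipped | Shortfall against one level down |
|---|---|---|---|---|
| 15 | 10 | 10 | none | 0% |
| 20 | 15 | 10 | 1 | 1 − 10/15 = 33% |
| 25 | 20 | 10 | 2 | 1 − 10/20 = 50% |
| 30 | 25 | 10 | 3 | 1 − 10/25 = 60% |

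The 10 mg/m² level is 10/22.5 = 44% of the earlier clofarabine dose.

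**3. Routes to 6 patients.** The MTD sentence needs a denominator of 6.

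- After 0/3 the level stays at 3 and the next one opens.
- After 1/3 it goes to 6. This is the only expansion the rules state.
- After 2/3 or 3/3 it closes.

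So only a level that had exactly 1 DLT in its first 3 patients has a stated path to qualify. The cleanest result, 0/3, does not. Nor do the rules say whether 1/6 permits escalation.

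**4. An example.** Take 0/3 at 15, 0/3 at 20 and 2/3 at 25, which uses 9 patients. As written, the next 3 go to 10 mg/m² (total 12), and 15 and 20 mg/m² keep 3 patients each. A conventional rule puts those 3 at 20 mg/m² (also 12), completing 6 there. The number of patients is the same, but only the second route tests the candidate MTD.

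**5. The timing gap.** Four weeks is day 28, and 42 − 28 = 14 days. The latest dated marrow is day 28 + 7 = 35, which is 42 − 35 = 7 days short of day 42. If a patient started *k* days before the last-entered patient, the gap for that patient is max(0, 14 − *k*) days. It is therefore 14 days at most for the last-entered patient and zero for anyone who started at least 14 days earlier.

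**The case against.** **Intent.** The 3+3 label and the cap of 4 × 6 point to a conventional design, and the MTD sentence itself tells staff that a candidate level needs 6 patients. The -1 step was probably written with failure at level 1 in mind. This stands as evidence of intent. It does not repair the text, because section X defers to section 2.1 for the rules.

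**Permitted routes.** The text closes only the failed dose. It does not forbid adding patients to a lower cleared level. After 0/3 at 10 mg/m² the escalation rule could be read as allowing 15 and then 20 to be re-entered; in the example that totals 9 + 3 + 3 + 3 = 18, within the cap. This stands too: the absence of an MTD is not forced. But the route is not spelled out, and it reaches the candidate level by way of two lower ones.

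**Stronger readings of the dose rule.** A reader might infer that most trials run under this text would misplace the dose. The documents do not support that. They give no DLT rates, and any percentage would depend on an assumed toxicity curve and on choices about 1/6 and re-escalation that the text leaves open. If staff run a conventional 3+3, the difference is nil. Nor do the documents show how Phase I was run, or that the dose rule is itself a safety risk: its error is toward a lower dose.

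**Timing.** Four weeks is a minimum and opening a level is optional, so waiting is allowed. Frequent blood counts would flag non-recovery, an unscheduled marrow could score the event, and a late DLT still counts toward the MTD. All of this stands and narrows the point. A reader might also treat all 3 patients in a cohort as unscored when the next level opens, but with staggered entry the earlier ones may already be past day 42. What remains is that nothing requires the wait.

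**Conclusion.** Both points hold as defects in the stated rules and should be fixed.

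(a) The de-escalation step is right only for failure at level 1. From 20, 25 or 30 mg/m² it skips one, two or three levels, and a level cleared at 0/3 has no stated route to the 6 patients that the MTD definition requires. This is a drafting gap in the rule that sets the CIA dose, and it rests on reading section 2.1 as written. Its effect on the selected dose cannot be quantified from the documents.

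(b) A higher level can open up to 14 days before the myelosuppression DLT can be scored in the last-entered patient, and no marrow is dated at day 42. This follows from the stated days without any assumption about DLT rates. It concerns only this one DLT and permits, rather than requires, early escalation.

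**What to change.** **1. Reword the dose rule in section 2.1**, for example: *If 2 or more patients at a level have a DLT, de-escalate to the next lower level (level -1 only if level 1 fails). 0/3 or 1/6 permits escalation. Any level to be declared the MTD, including level 4, is first expanded to 6 patients, within the maximum of 24.* The existing MTD definition can stay.

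**2. Add a timing condition.** Before a new level opens, require observation to day 42 for any leukemia-free patient at the current level whose counts have not recovered by week 4. Time the marrow that the DLT definition already implies at day 42 or later, and add it to the section V table. Patients with residual leukemia need not hold accrual, because this DLT requires its absence.

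**Cost.** Wording in sections 2.1 and V. Usually 3 more patients at the candidate level, within the cap. Five levels × 6 = 30 is the theoretical ceiling, but passing 24 would require levels 1, 2 and 3 each to clear at 0/3 and then each to show 2 or more DLTs in the next 3 patients. The wait adds up to about 2 weeks per newly opened level (3 × 2 = 6 weeks at most for levels 2 to 4), and one marrow for each patient concerned, only when such a patient exists.
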